6. PROCEDURES

* COVID-19 restrictions, if applicable: All interactions for the RCT with research staff will adhere to McMaster University's COVID-19 guidelines as well as government recommendations/protocols. As such, participants will be provided a combination of In Person/Zoom visits. Consent will most often be in person at the hospitals with research staff but if participants from the community choose to review consent over Zoom, they will be asked to sign consents through REDCap during the meeting. Zoom is an externally hosted cloud-based service (https://zoom.us/privacy-and-legal). Participants will be informed of the small risk of a privacy breach for data collected on Zoom. Participants will then be encouraged to express their concerns about using Zoom and be offered the alternative opportunity to participate via phone. An electronic copy of the consent or assent forms will be signed by participants on REDCap.

At the consent visit, regardless of method and site, participants will be fully informed of the protocol for each arm of the study (Usual Care and App group). Participants will also be informed of their chance (50%) of being assigned to either group. Due to the nature of the study participants and researchers are unable to be blinded to their study condition. Once consent is obtained, participants will be randomized to The Usual Care or The App group using computer generated codes. Those in The App group may be given their devices at the ED. Alternatively, if they can't stay for this they can come into The Institute for Applied Health Sciences (IAHS) within 2 days of consent to receive devices and download the App. If a participant is out of reasonable range to visit, devices may be mailed to them via FedEx within 1 day of providing consent and a Zoom meeting arranged to help download The App. If participants do not have an

iPhone above version 6, they will be provided an iPhone and an Apple Watch. They may choose to use their own iPhone if they have one with the appropriate model number. Participants will be informed that all devices supplied must be returned at the end of the study period.

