7. INTERVENTIONS

Participants randomized to the control group will be provided Usual Care which often is some type of gradual return guidelines the practice (ED, General Practitioner) subscribes to. These are usually provided in a paper format for the patient to take home. Participants in the Usual Care group will complete symptom surveys every 24 hours via REDCap. The Back2Play App requests symptom surveys be done 3 times daily (quickly done on the watch or phone). The Back2play App also asks users to go to the BrainGames App when participants indicate they are ready to progress to the next stage of RTS in the guidelines. In The BrainGames App they can complete 5 neuropsychological tasks that provide feedback about their readiness to progress. These tasks are not available for those in the Usual Care group.

Surveys about cognitive and physical activities engaged in as well as the participants self-rating of cognitive activity level (1-5) and stage of recovery (1-5/6) are done on a daily basis by both groups.

Participants who have been randomized to the App group will be asked to:

- Download The Back2Play App and The B2P BrainGames App on their iPhone and the Apple Watch provided either at the ED or at a scheduled baseline visit (within 2 days of concussion).
- Pair the Apple Watch to their iPhone and wear an Apple Watch for the duration of the study.
- Complete the initial post-concussion symptom survey on the App with the Research Assistant and receive orientation to The Back2Play App.
- Complete 3 symptom surveys per day on The Back2Play App (Morning, Afternoon and Evening) and daily surveys about cognitive and physical activities as well as self-rating of participants' own cognitive level of activity and stage of concussion recovery until 2 days following symptom resolution.
- Complete games on the B2P BrainGames App (i.e. matching games) which are suggested whenever the participant moves up a stage in RTS Protocol.
- Attend a Zoom Follow Up meeting 2 days after symptom resolution or after a maximum of 3 months of using The App. Here, we will ask participants questions about their perceptions of how well The App guided them through their recovery. Did they agree with classifications and notifications, did they understand the guidelines as well as questions about any other interventions they may have received. This Zoom visit will be recorded and saved to a secure, password encrypted study computer.

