- Complete the (SUS) after they have finished using the App (Appendix 1.5). Participate in a Follow Up interview (Appendix 1.6) which will assess the youth's experience with their recovery using The Back2Play App, ask about any other interventions they had and if they have experienced a repeat injury during the time in the study.
- Delete the App from their phone during this interview and arrange to return (by scheduled pick up or FedEx label sent by The Research Assistant) device(s).
- 3 months following study enrollment, participants will be sent a survey through REDCap about reinjury to complete.

Participants who have been randomized to the usual care group will be asked to:

- Receive the usual course of care given by the hospital, General Practitioner or clinic which may or may not include written guidelines, suggestions or resources
- Complete the initial post-concussive symptom survey with The Research Assistant.
- Complete symptom surveys and daily surveys about cognitive and physical activities as well as self-rating of participants' own cognitive level of activity and stage of concussion recovery every 24 hours emailed by REDCap until 2 days following symptom resolution.
- Participate in a Zoom visit 2 days after symptom resolution or after 3 months of
 participation for those who do not achieve symptom resolution. Participants will
 be asked questions regarding their knowledge of and ability to follow the Usual
 Care guidelines they received and about any other interventions they may have
 received. This Zoom visit will be recorded and saved to a secure, password
 encrypted study computer.
- 3 months following study enrollment, participants will be asked to complete a survey about reinjury.

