8. DESIGN

Phase 3 of this study has both quantitative and qualitative components. The aims of the qualitative components of the study are to determine if participants liked using The App, and if their experiences of using it helped their recovery from concussion. In addition, qualitative data will be used to review any improvement suggestions to The App before commercialization. Using both qualitative and quantitative research methods we will explore

the usability of The Back2Play App components under consideration for the final version of the App to be commercialized.

Primary Research Outcomes

To assess:

- Risk for repeat head injuries within three months of study completion (3-6 months after injury)
- Duration of symptoms: Time to symptom resolution from date of injury

Secondary Research Outcomes

To assess:

- 1) The frequency of symptoms using PCSS.
- 2) Time to return to activity and time to progress through the 6 stages of RTA
- 3) Perceptions of the platform by parents and youth.
- 4) Accuracy of the algorithm embedded in the background of The App classifying the participant's stage of recovery

Measures

Symptoms

Concussion symptoms will be assessed on The Back2Play App for those randomized to The App group and via REDCap for those randomized to Usual Care. A modified version of the PCSS (consisting of 22 symptoms) will be completed by youth in both groups. The Likert scale was modified to detect the presence of symptoms rather than symptom severity. Symptom data will be collected 3x/day for participants using The Back2Play App and every 24 hours for participants in the Usual Care group.

Cognitive Activity

Cognitive activity will be assessed using a modified version of the scale developed by Brown et al. Participants in both groups will be asked to complete this scale once per day through REDCAP which will appear as follows:

"Please rate 1-5 what you've been doing today"

- 1- None- No reading, homework, text messaging or screen time (T.V., cell phone), can talk on phone
- 2- Minimal- 15 minutes of screen time or schoolwork 2x daily. Socialize with 1-2 friends, no longer than 30 minutes,
- 3- Moderate- Homework in 15 minutes blocks for a maximum of 45 minutes. Screen time/T. V in 15-minute blocks, for up to an hour daily.
- 4- High- Complete as much homework as tolerated. 1 test/week or tests with accommodation (i.e. longer time to write), less reading, homework and screen time than normal
- 5- Full- no restrictions to cognitive activity

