9.5. DATA ANALYSIS PLAN

The recordings of online consent (Zoom), for Phase 3, will be stored on a study computer and saved to a secure password encrypted server. As described above, participants will be asked to complete the (SUS). The SUS yields a single number representing a composite measure of the overall usability of the system being studied. Adjustments and modifications to The Back2Play App will be made before commercializing the product.

We will collect and report descriptively all demographic information, injury-related data (type, mechanism of injury, numbers of injuries), youth premorbid health history. Descriptive statistics such as means, medians, and frequencies will be reported where appropriate. Baseline comparisons will be performed between those that use The App and those whose recovery involved Usual Care with variables of mechanism of injury, age, sex, school performance and concussion history. These variables will be-analyzed using Pearson Chi Squared Cross Tabulations, T-Test and ANCOVA, to ensure the groups are similar. We will also evaluate agreement of the algorithm with the self-reported stage of recovery participants input using these same statistics.

The dichotomous variable, repeat injuries (coded as yes or no), will be analyzed using multivariate logistic regression and resulting odds ratios to determine if using The Back2Play App decreases risk of repeat injury. Confounders of age, gender, number of symptoms, time since last injury and comorbidities of premorbid mental health issues or learning disabilities will be examined as to their potential impact on outcomes. Many of these variables will be correlated with each other and these correlations will need to be examined carefully before they are entered into the analyses.

Time to symptom resolution will be analyzed using survival curves with Multivariate Cox regression analysis. Cox regression (also called proportional hazard models) is a method of survival analysis that models the time until some event as a function of either continuous or categorical predictors, allowing for the fact that not all subjects will experience the events of interest and that they will occur at different times.

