Appendix 1.1 Business Rules for In-App Notifications

Progression through the CanChild RTA/RTS Guideline

- 1. Participants cannot enter RTA Stage 4 until they have completed RTS Stage 1-3
 - o If the participant reports RTA Stage 4 when they are in RTS Stage 1 or 2 they will receive the message "Stage 1, 2 and 3 come before RTA Stage 4!"
- 2. Participants must complete RTS Stage 5 (Full Return to School) before they can enter RTA Stage 4.
 - If the participant reports RTA Stage 4 or 5 when they are in RTS Stage 3 through 5, they will receive the message "You should complete RTS Stage 4-5 before RTA Stage 4-6".
- 3. Participants will be recommended to move to Stage 2 of RTS after 7 days
 - o If the participant reports RTS Stage 1 for 7 days, they will receive the message "You reported being in Stage 1 for 1 week, time to move to Stage 2!"
- 4. Participants will be recommended to move to Stage 3 of RTS after 14 days
 - o If the participant reports RTS Stage 2 for 14 days, they will receive the message "You reported being in Stage 2 for 2 weeks, time to move to Stage 3!"
- 5. Once in RTS Stage 3, participants cannot move back to Stage 2.
 - o If the participant reports RTS Stage 3 and moves back to RTS Stage 2, they will receive the message "Once your reach RTS Stage 3, you should not return to RTS Stage 2".

- 6. Participants are recommended to complete RTA and RTS Stage 1-3 together.
 - o If the participant reports RTA Stage 3 while in RTS Stage 1 or 2, they will receive the message "Remember, RTS and RTA Stage 1 to 3 should go together!"
- 7. Participants will be cautioned when they try and skip a stage
 - o If the participant skips from RTS Stage 2 to RTS Stage 4, they will receive the message "You forgot RTS Stage 3, we recommend you log this stage first!"
- 8. Participants will be cautioned when they try to move back a stage.
 - o If the participant moves back a Stage i.e., RTS Stage 5 to Stage 4, RTA 5 to Stage 4 they will receive the message "*Are you sure you want to move back a stage?*"
- 9. Participants cannot progress to a new stage of RTA/RTS if 2 or more symptoms worsen
 - o If the participant reports that 2 or more symptoms worsen (from morning to evening survey), **and** the participant attempts to progress to a new stage, they will receive the message "We recommend you do not progress to a new stage and inform a parent of your symptoms".

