- 10. Participants cannot progress to a new stage of RTA/RTS if their total number of symptoms increases by 2.
 - o If the participant reports an increase in symptoms by 2 (from morning to evening survey) **and** the participant attempts to progress to a new stage, they will receive the message "We recommend you do not progress to a new stage and inform a parent of your symptom".

CanChild RTA/RTS Symptom Strata

- 11. Participants will be classified to Strata A (Symptom Free within 48 hours after Injury) if their initial symptoms disappear within 24 hours or after 24-48 hours a participant reports ≤ 2 symptoms.
 - o If symptoms worsen, a participant can transition to Strata B.
 - o If the participant reports that their symptoms disappear within 24 hours, they will receive the message "Take at least 24 hours for each Stage as you complete the guidelines".
- 12. Participants will be classified to Strata B (Symptom Free/Symptoms decreases within 1-4 weeks post injury) if the report > 2 initial symptoms at 50 hours and continue at > 2 for 1 week (168 hours) up to 4 weeks. If the child's symptoms decrease, but are still >2, the child should remain in stratum B.
 - o Once a participant is in Strata B, they can never go to Strata A.
 - o If a participant is in Strata B and progressing through Stages within 2 days, but symptoms are getting worse, the child should take longer to progress through the stages.
 - o If > 2 Symptoms for a month, move the participant to Strata C

- o Recommendation: "Take at least 48 hours for each Stage as you complete the guidelines".
- 13. Participants will be classified to Strata C (Symptomatic for more than 4 weeks) if they report ≥ 2 initial symptoms for ≥ 4 weeks, or if the participant has been in Strata B for 1 month.
 - Once a participant is in Strata C, they can never go to Strata A or B.
 - o Recommendation: "Take at least 1 week for each Stage as you complete the guidelines".

Increasing or Worsening Symptoms

- 14. Participants will be reminded to share their symptoms with their parents if their number of symptoms increases by 2
 - o If the participant reports 2 or more symptoms new symptoms, they will receive the message "We recommend you inform a parent of your symptoms".
- 15. Participants will be reminded to share their symptoms with their parents if 2 or more symptoms worsen.
 - o If the participant reports 2 or more symptoms worsen, hey will receive the message "We recommend you inform a parent of your symptoms".

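### Time to symptom resolution, a primary outcome, has no dating rule, and the surveys that would date it run on different schedules by arm, so the hazard ratio may move with no true effect

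*Combined protocol and SAP*

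**What the plan says.** Section 8 lists as a primary outcome "Duration of symptoms: Time to symptom resolution from date of injury". Section 9.5 states: "Time to symptom resolution will be analyzed using survival curves with Multivariate Cox regression analysis".

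On collection, Section 8 (Measures, Symptoms) says: "Symptom data will be collected 3x/day for participants using The Back2Play App and every 24 hours for participants in the Usual Care group". Section 7 gives the App arm morning, afternoon and evening surveys. Usual Care completes its surveys "every 24 hours emailed by REDCap until 2 days following symptom resolution". Both arms use the same list of 22 symptoms, scored present or absent.

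Appendix 1.2 points to nearer two full symptom lists a day on the App. In the first block the midday list opens only after a bad answer to a global question, and the later blocks show symptom surveys in the morning and evening only. Sections 7 and 8 and rule 16 of Appendix 1.1 say three.

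Three things are not stated: the number of symptoms that counts as resolved, the record that gives the date, and whether the first clear record is enough or must be sustained. Sections 7 and 8 use symptom resolution to end the diary and to time the Zoom visit and the later reinjury question, but do not define it. Rule 11 of Appendix 1.1 puts a youth with up to 2 symptoms in its symptom-free stratum, but that rule only steers App notifications.

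**The concern.** With one survey a day, a day is either clear or not. With two or three, a day can count as clear if any survey is clear, or only if all are. For a youth whose symptoms come and go near recovery, these rules give different dates, and the difference arises in the App arm alone. The first rule brings App dates forward and the second puts them back, while Usual Care dates stay where they are.

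The hazard ratio for a primary outcome could therefore include a part that reflects only how often each arm was asked. The direction of that part would rest on a choice that the plan leaves open, in a trial where "participants and researchers are unable to be blinded to their study condition". The same undefined date also decides when each participant's diary stops.

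**Working it through.** **The plan's own figures.** The plan gives no event count or hazard ratio for this outcome. Its sample size rests on repeat head injury, and it reproduces. For 16% against 2% (mean 9%), two-sided 0.05, 80% power:

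n per arm = [1.96√(2×0.09×0.91) + 0.84√(0.16×0.84 + 0.02×0.98)]² / 0.14² = 64.4

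That is 65 per arm or 130 in total, against 128 stated; 128/0.80 = 160. The check below uses 64 per arm.

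**Precision.** With about 13% unresolved at three months (Section 2), events ≈ 128 × 0.87 = 111, so SE(log HR) ≈ 2/√111 = 0.19.

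**Null model.** There is no treatment effect. A survey on day d is clear if

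slope × (d − m) + √ρ × day effect + √(1−ρ) × survey effect > 0

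- From the documents: the personal recovery time m is log-normal, recalibrated in each cell so that the Usual Care record shows 50% unresolved at 30 days and 13.5% at 90 (Section 2 gives 50% at one month and 13 to 14% at three). The horizon is 90 days.
- Assumed, because the documents give nothing: within-day correlation ρ of 0.5, 0.8 or 0.95, and slope of 1.0, 0.3 or 0.1 per day. A youth passes from 2.5% to 97.5% clear in 2×1.96/slope = 3.9, 13 or 39 days.
- Also assumed: diary from day 1, two App surveys a day, one momentary Usual Care survey, and resolution dated at the first clear day.

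Null hazard ratios, App against Usual Care, at ρ = 0.5 / 0.8 / 0.95 (100,000 simulated youths measured under both schedules):

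| Recovery | Any survey clear | All surveys clear |
|---|---|---|
| Sharp (slope 1.0) | 1.010 / 1.007 / 1.003 | 0.988 / 0.993 / 0.996 |
| Moderate (0.3) | 1.028 / 1.019 / 1.010 | 0.958 / 0.975 / 0.988 |
| Slow (0.1) | 1.067 / 1.048 / 1.027 | 0.882 / 0.931 / 0.968 |

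**Scale.** The largest shifts are ln(1.067)/0.19 = 0.34 SE and |ln(0.882)|/0.19 = 0.66 SE. With slow recovery the median moves 1.3 to 2.8 days earlier (*any*) or 1.3 to 5.4 days later (*all*), and 2,000 null trials per cell reject in 6 to 10%. The 10% reduction in recovery time that Section 3 calls of interest is 3 days on an assumed 30-day course. Only slow recovery with the *all* rule reaches it.

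**Other assumptions.**
- Three App surveys, slow recovery: up to 1.104 (*any*) or down to 0.830 (*all*).
- Usual Care survey asking about the past 24 hours, two momentary App surveys, slow recovery: *any* 1.078 to 1.289. The top value is ln(1.289)/0.19 = 1.3 SE, with 28.9% rejection.
- A second model, fitted to the 59% and 14% also given in Section 2, with three App surveys and ρ from 0 to 0.8. At a transition scale of 7 days (slope 1/7 = 0.14): 1.06 to 1.08 (*any*) or 0.79 to 0.90 (*all*). At 14 days (slope 0.07): 1.10 to 1.15 or 0.65 to 0.84. This model was not recalibrated. At 14 days its Usual Care recorded median falls to about 19 days from a true 36, so its larger figures fit Section 2 less well.
- Time of day: in the second model at 7 days, with an assumed daily rhythm, the *any* rule gives 1.04 if the Usual Care survey is done in the morning and 1.22 if in the evening.

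**Does a remedy work?** Requiring two consecutive clear days without matching the records does not remove the shift (slow recovery: *any* 1.031 to 1.092, *all* 0.891 to 0.968). One matched daily record in both arms does: HR 0.990 to 1.006, rejection 4.3 to 6.2%.

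**The case against.** The strongest objection is that nothing in the documents shows the fluctuation that the shift needs. Rules 9, 10 and 16 of Appendix 1.1 may suggest it, since they act on change within a day. But they fire when two or more symptoms worsen or are added. They do not show a youth alternating between clear and not clear close to recovery. This stands: the fluctuation is a condition of the concern and has not been shown.

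Two stronger readings are tempting, and neither is supported.
- A reader might infer that the daily wording differs by arm, because an App survey asks how the youth feels that morning. That wording belongs to the first assessment, and Usual Care also completes an initial survey. The later App pages ask about current symptoms.
- A reader might take the 24-hour interval to mean that Usual Care is asked about the whole past day, which yields the largest figures. The interval is a frequency. No recall window is stated or excluded. Under that assumption the result also favours the App almost by construction, because Usual Care must then be clear throughout the day.

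Other points carry less weight. Frequent surveys are part of the intervention, but the outcome need not be dated from all of them. The stage of recovery is self-rated daily in both arms, and the interview asks everyone about remaining symptoms, but neither gives the date on which symptoms ended. Youths may enrol up to a month after injury, yet letting entry run to day 30 in the second model left similar shifts (1.07 and 0.88 at 7 days). The App shows yesterday's symptoms first, which might damp changes between surveys; this was not modelled. The introduction calls this phase a feasibility trial, but Section 8 still names this outcome as primary.

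**Conclusion.** The point holds in a conditional form. It is certain that resolution is undefined, that no source record is named, and that the planned survey schedule differs by arm. Whether this moves the hazard ratio depends on fluctuation within the day near recovery, for which the documents give no figure.

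The size is therefore unknown. It is negligible if resolution is sharp. With two App surveys, a momentary Usual Care survey and slow recovery, it reaches about 0.7 SE. That is not an upper bound, since three surveys, a different recall window or noisier recovery give more.

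A reader might conclude that the design favours the App, or that the result would be invalid. Neither follows: the direction depends on the missing rule, and in the calibrated model with a momentary Usual Care survey sharp or moderate recovery leaves the hazard ratio between 0.96 and 1.03. The plan should still be changed, because a primary time-to-event outcome needs one event definition applied alike in both arms, and the remedy is cheap.

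**What to change.** In Section 9.5, define resolution once for both arms: for example, 0 of 22 symptoms, dated at the first of two consecutive symptom-free daily records. Derive it from one once-daily record in each arm: the App's evening symptom survey, and the Usual Care REDCap survey set to the same evening timing, wording, recall window and missed-survey handling. Matching frequency alone is not enough. If Usual Care were asked about the past 24 hours, the App evening survey alone would still give null hazard ratios of 1.02 to 1.21 with moderate to slow recovery.

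Use the same rule to end the diary and to trigger the Zoom visit. Keep the other App entries for notifications and description.

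The cost is a protocol amendment, a short derivation rule and a small change to the REDCap survey; neither arm gets an extra survey. The drawbacks are that morning and midday App entries drop out of the primary analysis, and that the date then depends on one daily survey that may be missed.

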4. INCLUSION AND EXCLUSION CRITERIA

Inclusion Criteria

Youth aged 10-18 at the time of injury will be included in this proposal. Youth must have had an impact to the head or body and diagnosed with a concussion by a physician. The youth must be symptomatic on admission to the study, and be within the first month of their initial injury. In addition, youth and their parents/guardians must be able to understand and complete questionnaires in English or French.

Exclusion criteria: Youth will be excluded from the study if they 1) have a confirmed significant brain injury requiring resuscitation, 2) were admitted to the pediatric critical care unit or surgical intervention, and 3) if they suffered a concussion but are no longer symptomatic, 4) they have been admitted to the PICU and 5) have been diagnosed with a developmental disability.

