
Cognitive and Physical Activities

Engagement in cognitive and physical activities will be measured once per day in those using the App as well as for those in the Usual Care group. The activities surveyed will match those recommended for each stage of RTA/RTS (Appendix 1.2)

Time to Stage

Participants in both groups will report their stage of RTA/RTS. The time from injury to each stage will be used to determine the time to stage and completion of the RTA/RTS guidelines.

Rate of Reinjury

All participants be asked at study completion and 3 months after symptom resolution if they have hit their head again in such a way that they experienced symptom exacerbation or return of symptoms for more than one day, if they moved back a stage in the guidelines for recovery, or if they sought medical care from hitting their head since the initial injury.

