Daily Symptom survey Page 1: Current symptoms - App generates what was reported yesterday - Global "How are you" question Page 2: New Symptoms	"Please select what cognitive activities you have been doing today" 1- School work 2- Computer time 3- Socialize with friends 4- Text/phone friends 5- Watch video or tv 6- Play a video game 7- Play a board game 8- Read a book 9- Puzzles 10- Other	"Please rate 1-5 what you've been doing today" Cognitive Scale "What Stage of the RTS protocol are you in? Sele 1, 2, 3, 4, 5" "What Stage of the RTA protocol are you in? Sele 1, 2, 3, 4, 5" "What physical activities did you do today?" 1. Brisk Walk 2. Swim 3. Stretch/Yoga 4. Play Catch 5. Walk around the mall/grocery store 6. Walk to the bus/car 7. Move around/clean your room 8. Other "Daily Symptom survey"	
Stage Three			
Page 1: Current symptoms - App generates what was reported yesterday	"Please select what cognitive activities you have been doing today" 1. School work	"Please rate 1-5 what you've been doing today" Cognitive Scale "What Stage of the RTS protocol are you in? Select: 1, 2, 3, 4, 5"	

	 Use iPhone Apps i.e. Snapchat Play on the iPad Watch T.V. Watch a YouTube video Watch a movie Play video games Play a board game Read/Re-read a book Listen to music Puzzles Other 	1, 2, 3, 4, 5" "What physical activities did you do today?" 1. Walk 2. Jog 3. Bike 4. Hike 5. Swim 6. Stretch/Yoga 7. Skate 8. Play Catch 9. Passing, shooting drills 10. Dribbling/Stickhandling 11. Other "Daily Symptom survey"

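### Time to stage runs from injury, but stages reached before enrolment are undated or datable only to the first report, and the plan does not say how to handle them.

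*Combined protocol and SAP*

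**What the plan says.** Section 8 (Design), under Time to Stage, sets the measure: "Participants in both groups will report their stage of RTA/RTS", and "The time from injury to each stage will be used to determine the time to stage". It serves the second secondary outcome, "Time to return to activity and time to progress through the 6 stages of RTA".

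Section 4 sets the entry window: "The youth must be symptomatic on admission to the study, and be within the first month of their initial injury". Section 5 also recruits through schools, coaches and concussion clinics, and lets families consent later with no time limit.

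The in-App surveys in Appendix 1.2 ask "What Stage of the RTS protocol are you in", with the same question for RTA. Section 7 has Usual Care participants report their stage every 24 hours once enrolled. Neither the surveys shown, nor the baseline data listed in section 9.5, nor the interview guide in Appendix 1.6 asks when a stage began.

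Two statements bear on how soon follow-up starts. Section 7 has App participants download the apps onto a phone and watch "provided either at the ED or at a scheduled baseline visit (within 2 days of concussion". Section 6 says those who cannot wait in the ED come in "within 2 days of consent to receive devices and download the App". The first counts from injury and the second from consent.

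Section 9.5 names Cox regression for symptom resolution and gives no method for time to stage.

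**The concern.** A youth enrolled two or three weeks after injury may already have moved through several stages. The measure needs the date each stage was reached, and the data collection shown starts only at enrolment. Such a youth can be in one of two positions for any stage from 2 upwards. (Stage 1 can reasonably be taken to start at injury.)

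- The stage was passed before enrolment, so no date exists.
- The stage is the one held at enrolment, so the only date on file is that of the first report. If that date is used, the time is too long.

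For late entrants the early-stage times would then partly measure recruitment delay, and early and late entrants would not be comparable. The App cannot influence a stage reached before randomisation. Including those stages in the comparison of arms therefore adds delay unrelated to treatment.

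This differs from time to symptom resolution. Entrants must be symptomatic, so resolution of the presenting symptoms cannot come before entry, but a change of stage can.

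**Working it through.** **The plan's own figures.** The plan gives no distribution of entry delay or stage duration, so there is no figure to reproduce. Its sample size rests on repeat head injury and is not affected.

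**One youth.** Suppose injury on day 0, RTS Stage 2 on day 3, Stage 3 on day 9 and enrolment on day 20. The first survey records Stage 3 on day 20. Used as the date of Stage 3, that is 20 − 9 = 11 days late. Stage 2 has no date.

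**Inputs for a range**
- Entry window: up to about 30 days (section 4).
- Stage times A: RTS Stage 2 at day 7 and Stage 3 at day 7 + 14 = 21, borrowed from the prompts in Appendix 1.1, rules 3 and 4.
- Stage times B: 48 hours per stage, so days 2 and 4, from the message in rule 12.
- Entry pattern, assumed: even over 0 to 30 days, or exponential with mean 7 days and delays above 30 set to 30.

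The stage times are assumptions too. The prompts fire on in-App reports, so they cannot act before enrolment, and rules 3 and 4 concern RTS while the outcome names RTA. They serve only as plausible values.

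**Formulas for Stage 2.** Let E be the entry delay, t2 and t3 the days Stages 2 and 3 are reached, and w = t3 − t2. The time is late by E − t2 if t2 < E ≤ t3, and missing if E > t3.
- Even entry: late share w/30; mean lateness w/2; missing share (30 − t3)/30.
- Exponential entry: late share exp(−t2/7) − exp(−t3/7); mean lateness 7 − w·exp(−w/7)/(1 − exp(−w/7)); missing share exp(−t3/7).

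| Stage times | Entry | Late | Mean lateness | Missing |
|---|---|---|---|---|
| 7, 21 | even | 14/30 = 47% | 14/2 = 7.0 d | 9/30 = 30% |
| 7, 21 | exponential | 0.368 − 0.050 = 32% | 7 − 14×0.135/0.865 = 4.8 d | 5% |
| 2, 4 | even | 2/30 = 7% | 2/2 = 1.0 d | 26/30 = 87% |
| 2, 4 | exponential | 0.7515 − 0.5647 = 19% | 7 − 2×0.7515/0.2485 = 0.95 d | 56.5% |

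**Everyone enters within 2 days.** Then E ≤ 2 ≤ t2 in both cases, so nothing is late or missing.

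**Variable stage durations.** A simulation of 400,000 youth used exponential stage durations with a mean of 3 or 7 days:
- Entry even over 30 days: Stage 2 is missing in 80% or 55%, and late in 10% or 22% by 3.0 or 6.0 days.
- Entry even over 14 days: missing in 59% or 27%, and late in 20% or 30% by 2.7 or 3.8 days.
- Entry within 2 days: missing in 5% or 1%, and late in 22% or 12% by 0.6 to 0.7 days.

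**The case against.** **Section 7 puts App set-up within 2 days of the concussion, where the problem nearly vanishes.** True if it governs entry. But it appears only in the App group's list, no matching limit is stated for Usual Care, and it conflicts with the one-month window in section 4 and the count from consent in section 6.

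**The plan never says a stage is dated to its first report.** Correct. Late dating is an inference from what is collected. The missing dates do not depend on it. The Usual Care form is not reproduced, so the absence of a start date is less certain in that arm.

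**Randomisation balances entry delay.** It does on average. A reader might infer that the comparison of arms is biased, but the documents do not show that. Bias would need first-report timing to differ by arm, for instance through device delivery. Balance does not supply missing dates, nor does adjusting for time since last injury, which section 9.5 lists for the repeat-injury regression.

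**Recalled dates would not reveal an App effect.** This stands. Those stages precede randomisation, so even perfect dates would show none. Recall helps only the description of time from injury.

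**The reach is limited.** This also stands. Entrants must be symptomatic, and section 2 says the guidelines bar high-level activity and contact sport while symptoms persist. Full return to activity should rarely precede entry.

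**Conclusion.** The gap is real but limited to one secondary outcome. As written, time from injury to stage cannot be obtained for stages reached before enrolment, and no rule covers them. In the scenarios with entry spread over a month, the Stage 2 time is missing in 5% to 87% of youth. It is late in 7% to 47%, by about 1 to 7 days if the first-report date is used. With slow progression both problems occur. At 48 hours per stage the problem is mainly missing dates. With entry within 2 days it is about nil at 48 hours per stage or slower, and small if stage durations vary. Entry pattern and stage times are assumed throughout.

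A reader might add the late and missing groups together and conclude that, under even entry and days 7 and 21, 77% of youth (47% + 30%) get a late Stage 2 time. That is wrong: the 30% already in Stage 3 have no Stage 2 time at all. Nor do the documents support reading this as a threat to the primary outcomes or the sample size, or to time to full return to activity beyond a small degree.

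**What to change.** 1. Record the current RTA and RTS stage in both arms at consent, before randomisation.
2. Compare arms only on stages above the entry stage, with time running from randomisation and adjustment for entry stage. State this as the method for the second secondary outcome.
3. For descriptive times from injury, also ask the date the current stage began. Allow the answers *not following stages* and *unknown*, since Usual Care may not include written guidelines.
4. Treat any stage at or below the entry stage without a date as reached before enrolment (left-censored), never as reached on the first survey date.
5. Reconcile sections 4, 6 and 7 on the time from injury to the start of follow-up, for both arms.

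The cost is one or two items at a contact both arms already have, plus analysis wording. The downsides are some recall error in the descriptive times, and late entrants contributing less to early-stage comparisons.
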